#### **Prospective Study**

The prospective part of this study will involve recruiting patients in the Emergency Department and offering them the opportunity to use DEXCOM G6 CGM instead of hourly fingerstick point of care glucose testing . We will enroll additional 50 non-critically ill DKA patients who will have glucose levels monitored via DEXCOM CGM and be treated in the stepdown unit. The primary outcome is time to resolution of metabolic acidosis. Secondary outcomes are length of ICU stay, length of hospital stay, frequency of hypoglycemic episodes defined as glucose level <70 mg/dl and cost savings.

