### Study Design:

#### Retrospective Quality Improvement Data

In January 2021 during COVID 19 pandemic, we launched a quality improvement project with goal to treat non-critically ill DKA patients outside of ICU setting in order to reallocate ICU beds for critically ill patients at New York Presbyterian Hospital /Columbia University Irving Medical Center. Before this quality improvement project, DKA patients were treated in the ICU setting because the DKA protocol requires hourly fingerstick glucose monitoring, which is considered higher level of care and not appropriate for stepdown unit or medical/surgical wards. During this quality improvement project, we monitored glucose levels remotely with continuous glucose monitoring (CGM) device DEXCOM G6 thus eliminating the need for hourly fingerstick glucose testing. Therefore, patients with DKA whose glucose levels have been monitored via DEXCOM G6 CGM have been treated in the stepdown unit instead of the ICU setting where glucose levels are monitoring hourly via fingerstick point of care glucose testing. We enrolled 48 patients (with additional 2 patients who had glucose levels monitored with CGM but were treated in the ICU setting therefore will not be used for this analysis).

Study participants were not being recruited and asked for their participation; non-critically ill DKA patients who presented in DKA had glucose levels monitored via CGM. Given that the recommended hourly fingerstick checks needed for treatment could not be performed on the stepdown unit and only in the ICU, the Dexcom G6 CGM device eliminated the need for hourly fingerstick checks and thus removed the barrier for patients being admitted to stepdown. Once the number of COVID cases decreased and ICU beds were more readily available, the hospital returned to practicing the pre-COVID standard of care, which was admitting DKA patient to the ICU for hourly glucose monitoring and we stopped enrolling patients for this retrospective quality improvement project

We propose to study outcomes of DKA patients who had glucose levels monitored with DEXCOM G6 CGM treated in the stepdown unit. The primary outcome is time to resolution of metabolic acidosis. Secondary outcomes are length of ICU stay, length of hospital stay, frequency of hypoglycemic episodes defined as glucose level <70 mg/dl and cost savings

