# Statistical Procedures:

The primary outcome for this study is the time to resolution of DKA. We will compare time to resolution of the DKA of patients who had glucose levels monitored via DEXCOM G6 CGM and treated in the stepdown unit (both those enrolled in the retrospective study and those who will be enrolled in the prospective study) to DKA patients who had glucose levels monitored hourly via fingerstick (and not CGM) and treated in the ICU setting.

We will perform a non-inferiority trial to study whether monitoring glucose levels via CGM in DKA patients treated in the stepdown unit is not inferior to DKA treated patients in the ICU setting with hourly fingerstick glucose monitoring.

For a noninferiority trial, based on what we have previously observed for the time to resolution of DKA, and a noninferiority margin of 1/2 the SD, we estimate that a sample size of 98 patients per group will have a 90% power to determine noninferiority at an alpha level of 0.05. Since we enrolled 48 patients in the retrospective part of the study, we will need additional 50 patients enrolled in the prospective part of the study to have 90% power and a noninferiority at an alpha level of 0.05. We plan a conservative approach where we will enroll additional 50 DKA patients who will have glucose levels monitored via CGM. We will compare with the historical control using 1:1 matching, thus will collect historical control data which include DKA patients treated for DKA in the ICU setting with hourly fingerstick glucose monitoring.

We will perform linear regression (for patients enrolled in both retrospective and prospective part of the study) to learn what clinical factors are associated with length of time to the DKA resolution. Then we will use propensity matching for historical control group (DKA patients treated in the ICU setting with glucose levels monitored via hourly fingerstick glucose levels).

To study the frequency of hypoglycemic episodes (<70 mg/dl) in patients from both prospective and retrospective study; we will use CGM glucose data stored manufacture's web based software : Clarity.

We will also evaluate frequency of hypoglycemic episodes (glucose level <70%) in historical control patients who were treated for DKA in the ICU and had hourly glucose level monitoring.

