- 3. Once glucose levels are transmitted to the study smartphone devices, glucose levels from the CGM to guide insulin adjustments. Check fingerstick glucose if CGM glucose levels are <100 mg/dl and >350 mg/dl to guide treatment decisions. Note that CGM device will have audible alerts if glucose level are < 100 mg/dl and >350 mg/dl. If there are NO glucose levels transmitted to the phone please check q 1 fingerstick glucose levels and contact [name] ([name]). If CGM glucose data cannot restored and patient needs g 1 hour fingerstick glucose testing, patient will be transferred to the ICU. If patient is moved to the ICU the CGM will be removed. Although CGM data will be transmitted to the study smartphone devices continuously, please monitor CGM glucose levels every 1 hour and make treatment decisions based on q 1-hour CGM readings or more frequently when glucose levels are <70 mg/dl (confirmed with a fingerstick glucose). If patient's glucose levels are <100 mg/dl on the CGM, fingerstick glucose testing will be performed to ensure that fingerstick glucose level is not in hypoglycemic range (<70 mg/dl). If patient's glucose levels are in hypoglycemic range (<70 mg/dl), fingerstick glucose levels testing will be performed as per hospital protocol until hypoglycemia resolves. Once hypoglycemia resolves, then glucose levels from the CGM can be used for further insulin adjustments. In the Emergency Department, document glucose levels q 2 hours as per the research protocol or more frequently as per provider request treating the patient. When patient is transferred to the stepdown unit, glucose levels should be recorded every 3 hours in hospital electronic medical record system.
- 4. If the patient condition worsens and patient requires the ICU care, patient will be transferred to the ICU. Also, if patient needs to get MRI or CT, sensor and transmitter will be removed prior to the imaging.
- 5. Smartphones which are receiving glucose data (study provider smart phone, study nurse smart phone and the study patient smart phone which receives glucose level from the sensor and is next to the IV insulin bag) should be transferred to the Stepdown Unit nurse when patient is arrives at the Stepdown Unit.

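### A shorter ICU stay in the CGM group is built into how the groups are defined, and excluding ICU-treated CGM patients overstates the ICU time and cost saved

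*Combined protocol and SAP*

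**What the plan says.** Under Study Design, the Retrospective Quality Improvement Data and Prospective Study sections give the same list of secondary outcomes, which begins: "Secondary outcomes are length of ICU stay, length of hospital stay". Hypoglycemic episodes and cost savings complete the list.

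The groups are defined by where patients were treated:

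- **Prospective CGM patients** (50 planned) will "have glucose levels monitored via DEXCOM CGM and be treated in the stepdown unit".
- **Retrospective CGM patients** number 48, all treated in stepdown. The same section mentions "additional 2 patients who had glucose levels monitored with CGM but were treated in the ICU setting therefore will not be used for this analysis".
- **Controls**, under Statistical Procedures, come from "historical control data which include DKA patients treated for DKA in the ICU setting with hourly fingerstick glucose monitoring", matched 1:1.

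The retrospective section explains that DKA patients went to the ICU before the project because hourly fingersticks were not considered suitable for stepdown or the wards.

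Under Study Procedures, Prospective Study, workflow steps 3 and 4 send a CGM patient to the ICU if the glucose signal cannot be restored and hourly fingersticks are needed, or if the patient's condition worsens. On the device, step 3 adds: "If patient is moved to the ICU the CGM will be removed". Nothing there says how such a patient is analysed.

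Statistical Procedures describes analyses for time to resolution, hypoglycemia, cost and nurse satisfaction. It gives none for length of ICU stay. The cost comparison uses the daily cost of ICU and of stepdown care, plus the cost of the device.

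**The concern.** An outcome can show an effect of an intervention only if group membership does not already settle it. Here each control has ICU time above zero because ICU treatment is the entry condition. Each CGM patient begins outside the ICU because stepdown treatment is the entry condition. In the retrospective cohort, two patients are removed for being in the ICU, which is a removal on the outcome itself. Propensity matching cannot repair this, since no eligible control can have zero ICU time.

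Two things are at stake. A small p-value for ICU stay could be reported as evidence that CGM shortens ICU stay, when it only restates where each group was placed. And the resource case for the strategy (ICU beds freed, money saved) would leave out the CGM patients who used ICU beds anyway, so both savings would be overstated. How often a CGM patient was nevertheless treated in the ICU bears directly on the study's rationale, yet it is not a listed outcome.

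**Working it through.** The plan gives no expected ICU stay, transfer rate or test for this outcome, so it has no figure of its own to reproduce. The sample size of 98 per group concerns time to resolution, and this point does not depend on it.

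**1. Group definitions side by side**

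| Group | Entry condition | ICU stay |
|---|---|---|
| Retrospective CGM, 48 | Treated in stepdown; 2 ICU-treated patients removed | Zero, unless one of the 48 later entered the ICU (not stated) |
| Prospective CGM, 50 | To be treated in stepdown | Zero unless transferred under step 3 or 4 |
| Controls, 98 | Treated in the ICU | Above zero for all |

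**2. How far transfers could move the difference**

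Inputs from the plan: 48 + 50 = 98 CGM patients and 98 matched controls. Assumptions: control mean ICU stay m of 1, 2 or 3 days; t prospective patients transferred, kept in the CGM group, each with a control-like ICU stay; zero ICU time for the rest.

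Expected difference (CGM minus control) = −m × (1 − t/98).

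| t of 50 | 1 − t/98 | m = 1 | m = 2 | m = 3 |
|---|---|---|---|---|
| 0 | 1.00 | −1.0 | −2.0 | −3.0 |
| 5 | 0.95 | −0.95 | −1.90 | −2.85 |
| 10 | 0.90 | −0.90 | −1.80 | −2.69 |
| 20 | 0.80 | −0.80 | −1.59 | −2.39 |

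The size moves with the transfer share; the sign does not.

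**3. What a test would show**

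With 20 transfers, 78 of 98 CGM patients (80%) have zero ICU time and rank below every control. The chance that a random control exceeds a random CGM patient is 78/98 + (20/98) × 0.5 = 0.90, against 0.50 under no difference. A simulation (lognormal stays with log-SD 0.7; t = 0, 2, 5, 10, 20; m = 1, 2, 3; Mann-Whitney test at 0.05; 1000 runs per scenario) rejected in 100% of runs in all 15 scenarios.

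**4. The ICU-treated CGM patients**

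First cohort: 48 + 2 = 50 patients monitored with CGM, of whom 2 were treated in the ICU. 2/50 = 4%. Clopper-Pearson limits: the 2.5% point of Beta(2, 49) is 0.0049 and the 97.5% point of Beta(3, 48) is 0.137, giving 0.5% to 13.7%.

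**5. Effect of the exclusion on the saving**

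Assume again that ICU-treated CGM patients have control-like ICU stays. With the two restored, the CGM group is 98 + 2 = 100, and the mean ICU time saved per patient is m × (1 − (2 + t)/100):

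- t = 0: 0.98m, against 1.00m with the two excluded. The overstatement is 2% of the control mean.
- t = 20: 0.78m if all are kept, against 1.00m if all 22 are dropped. The overstatement is 22% of the control mean.

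The known exclusion alone costs little. The larger exposure is the unwritten rule for prospective transfers.

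**The case against.** The strongest reply is that this is a contrast of two care-location strategies. Controls were in the ICU because the fingerstick schedule required it, so their ICU time is a consequence of the comparator strategy. They are selected on ICU entry, not on length of stay. ICU time avoided is what the project was set up to achieve, and a cost comparison between ICU and stepdown care rightly includes it. That stands, and it is why ICU stay should be relabelled and kept.

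It is also fair that no test of ICU stay is written. A between-group comparison is implied by the historical-control design and the cost comparison, but a p-value is not promised. The point is therefore to settle the status of this outcome before analysis.

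Three stronger readings are tempting, and the documents do not support them:

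- **That CGM patients have zero ICU time by construction.** Workflow steps 3 and 4 allow transfer in the prospective part, and no passage removes transferred patients from analysis. The sentence about taking off the CGM concerns the device, not the analysis set.
- **That the comparison carries no information.** Only its direction is settled. Its size depends on the control stay and on how many CGM patients used the ICU.
- **That 2/50 is a failure or transfer rate.** The text says only that two patients were treated in the ICU. It does not say that they began in stepdown, or why they were in the ICU.

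What the reply does not answer is the exclusion of CGM patients because of ICU treatment. Even as pure resource use, ICU time saved has to be net of the ICU time that CGM patients used.

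**Conclusion.** The concern holds in limited form. That the CGM group will show the shorter ICU stay follows from the group definitions, so a significance test of that difference would say nothing about an effect of CGM. Excluding ICU-treated CGM patients overstates the ICU and cost savings: by about 2% of the control mean stay for the two known patients, and by up to 22% if 20 prospective transfers were also dropped. Both percentages assume control-like ICU stays, and the 20 is illustrative; the documents give neither stays nor a prospective transfer rate. The finding on direction needs only that most CGM patients remain outside the ICU.

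The size of the difference keeps its value as descriptive resource use. A reader should not conclude that the outcome is worthless or that the cost comparison is invalid. This concerns secondary outcomes and leaves the definition of the primary outcome untouched.

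**What to change.** Amend the two outcome lists under Study Design, and Statistical Procedures including its cost paragraph, as follows:

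1. For ICU use and cost, keep all CGM-started patients in the CGM group, including the two excluded retrospective patients and any prospective patient transferred to the ICU. Make this the main analysis, or at least a sensitivity analysis.
2. Report the proportion of CGM patients treated in the ICU with an exact confidence interval, and their ICU hours. Describe the first cohort's 2/50 as a proportion treated in the ICU, without calling it a failure rate.
3. Label length of ICU stay as descriptive resource use with no between-group test. Use length of hospital stay, already listed and not fixed by either group's definition, for the between-group comparison.
4. In the cost analysis, charge the CGM group for the ICU time its patients actually used.

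The cost is wording, plus ICU entry and exit times for CGM patients from the records the study already plans to review. Sample size and patient care are unchanged. The downside is that the reported ICU and cost savings become somewhat smaller, and ICU stay can no longer be presented as a tested result.

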# Inclusion Criteria:

age >18, AG>20 (normal is 5-17) with bicarbonate <19 (normal is 19-27), positive urine ketones or beta hydroxybutyrate >0.3 (normal is <0.27)

glucose level >250 mg/dl on presentation to the ED

# Exclusion criteria:

hypotension (BP below 80/60), require pressor therapy, or have any contraindication for utilizing Dexcom CGM ,, altered mental status, lack of decision making capacity, mechanical ventilation or non-invasive ventilation, chronic kidney disease with GFR <30 including patients with hemodialysis, pregnancy, other clinical reason for admission to the intensive care unit (ICU) , are excluded from study participation

# Provider Survey/nurses satisfaction

We will study nurses' satisfaction evaluating remote glucose monitoring in DKA patients using DEXCOM G6 CGM by administering an anonymous online survey. We will evaluate nurses' satisfaction only for the prospective part of the study.

# Statistical Procedures:

The primary outcome for this study is the time to resolution of DKA. We will compare time to resolution of the DKA of patients who had glucose levels monitored via DEXCOM G6 CGM and treated in the stepdown unit (both those enrolled in the retrospective study and those who will be enrolled in the prospective study) to DKA patients who had glucose levels monitored hourly via fingerstick (and not CGM) and treated in the ICU setting.

We will perform a non-inferiority trial to study whether monitoring glucose levels via CGM in DKA patients treated in the stepdown unit is not inferior to DKA treated patients in the ICU setting with hourly fingerstick glucose monitoring.

For a noninferiority trial, based on what we have previously observed for the time to resolution of DKA, and a noninferiority margin of 1/2 the SD, we estimate that a sample size of 98 patients per group will have a 90% power to determine noninferiority at an alpha level of 0.05. Since we enrolled 48 patients in the retrospective part of the study, we will need additional 50 patients enrolled in the prospective part of the study to have 90% power and a noninferiority at an alpha level of 0.05. We plan a conservative approach where we will enroll additional 50 DKA patients who will have glucose levels monitored via CGM. We will compare with the historical control using 1:1 matching, thus will collect historical control data which include DKA patients treated for DKA in the ICU setting with hourly fingerstick glucose monitoring.

We will perform linear regression (for patients enrolled in both retrospective and prospective part of the study) to learn what clinical factors are associated with length of time to the DKA resolution. Then we will use propensity matching for historical control group (DKA patients treated in the ICU setting with glucose levels monitored via hourly fingerstick glucose levels).

To study the frequency of hypoglycemic episodes (<70 mg/dl) in patients from both prospective and retrospective study; we will use CGM glucose data stored manufacture's web based software : Clarity.

We will also evaluate frequency of hypoglycemic episodes (glucose level <70%) in historical control patients who were treated for DKA in the ICU and had hourly glucose level monitoring.

We will evaluate potential cost savings comparing treatment of DKA patients in the stepdown unit using DEXCOM G6 CGM (both retrospective quality improvement project and prospective study vs treatment of DKA patients in the ICU setting using hourly point of care glucose testing (historical controls). We will include variables such as daily cost of ICU stay vs stepdown unit, cost of DEXCOM CGM.

We will calculate satisfaction scores from nursing surveys for the prospective part of the study.

There are no validated surveys assessing provider satisfaction as use of CGM in the inpatient setting is still a novel approach. We will use a modified CGM survey used for patient/caregivers (11)

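### The plan has no rule for prospective CGM patients moved to the ICU: the group wording would let them be dropped, and if they are kept, the stated hypoglycemia source misses their later episodes

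*Combined protocol and SAP*

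**What the plan says.** Statistical Procedures compares time to DKA resolution in "patients who had glucose levels monitored via DEXCOM G6 CGM and treated in the stepdown unit" with historical controls treated in the ICU on hourly fingersticks. A parenthesis straight after the quoted words says that this group takes in the people enrolled in both the retrospective and the prospective parts. The Study Design paragraph on the prospective part describes the 50 new patients as those "who will have glucose levels monitored via DEXCOM CGM and be treated in the stepdown unit", and adds: "Secondary outcomes are length of ICU stay, length of hospital stay", followed by hypoglycemia below 70 mg/dl and cost savings.

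Study Procedures, Prospective Study, gives two routes out of stepdown. Item 3 covers signal loss: "If CGM glucose data cannot restored and patient needs g 1 hour fingerstick glucose testing, patient will be transferred to the ICU". Item 4 covers deterioration: "If the patient condition worsens and patient requires the ICU care, patient will be transferred to the ICU". Item 3 also says: "If patient is moved to the ICU the CGM will be removed". That sentence sits under signal loss, but its wording covers any move to the ICU.

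For hypoglycemia in the CGM group, Statistical Procedures names one source: "in patients from both prospective and retrospective study; we will use CGM glucose data stored" in the manufacturer's Clarity software. Hypoglycemia is also to be evaluated in the controls, who had hourly glucose monitoring in the ICU.

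In the retrospective part, two further CGM patients, counted outside the 48, "were treated in the ICU setting therefore will not be used for this analysis".

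**The concern.** The protocol foresees transfer to the ICU but gives no analysis rule for it. A transferred patient was enrolled, was monitored by CGM for a time and was on stepdown for a time, so meets the group definition only in part. There are two consequences, and for any one patient they are alternatives.

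- **If the patient is dropped**, the CGM group is selected on something that happened after enrolment. Patients moved because they worsened may well resolve more slowly. Losing them would shorten the CGM group's mean time and favour non-inferiority. Their ICU days would also leave the ICU-stay and cost comparisons.
- **If the patient is kept**, the primary comparison is protected, but hypoglycemia after the CGM record ends has no stated source. The count then has a gap in one group only. Study Purpose and Rationale names hypoglycemia, beside time to resolution, as a measure on which CGM is to be shown non-inferior, so this is not a marginal endpoint.

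**Working it through.** **The plan's own figure.** Inputs from Statistical Procedures: margin 0.5 SD, 90% power, alpha 0.05 (sidedness not stated), 98 per group. With n = 2 × ((z for alpha + z for power) / 0.5)²:

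- one-sided 0.05: 2 × ((1.645 + 1.282) / 0.5)² = 68.5, so 69 per group;
- one-sided 0.025: 2 × ((1.960 + 1.282) / 0.5)² = 84.1, so 85 per group.

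Neither gives 98. That is a separate matter and does not affect this point. At 98 per group, power is 96.8% (one-sided 0.05) or 93.8% (one-sided 0.025). With 96 it is 96.6% or 93.4%, so losing two patients costs almost no power. The issue is bias.

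**Bias if transfers are dropped.** The documents give neither the number of transfers nor their delay, so both are assumed. Let k be the number dropped and d their excess time to resolution, in SD, over those who stay. Suppose the true difference with all 98 kept equals the margin, and the test is one-sided at 0.05.

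- Shift in the CGM mean = (k/98) × d.
- Standard error with k matched pairs removed = √(2/(98 − k)).
- Chance of wrongly declaring non-inferiority = 1 − Φ(1.645 − shift/SE).

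For k = 2, SE = √(2/96) = 0.1443:

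- d = 1: shift = 0.0204; 0.0204/0.1443 = 0.141; error = 6.6%.
- d = 2: shift = 0.0408; 0.0408/0.1443 = 0.283; error = 8.7%.

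For k = 7, SE = √(2/91) = 0.1482. The range is then:

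| Dropped | d = 0 | d = 0.5 | d = 1 | d = 2 |
|---|---|---|---|---|
| 2 of 98 | 5.0% | 5.8% | 6.6% | 8.7% |
| 7 of 98 | 5.0% | 8.0% | 12.2% | 24.8% |

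At one-sided 0.025, k = 2 gives 3.4% (d = 1) and 4.7% (d = 2).

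These are upper figures for each k and d, because the calculation treats the controls removed with the dropped patients as average. If matching carried half the excess into those controls (also assumed), the shift halves. The k = 2 results become 5.8% and 6.6%, and the k = 7 results 8.0% and 12.2%.

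**Dilution if transfers are kept.** If ICU care made two retained transfers resolve exactly like controls, the difference becomes 0.5 × 96/98 = 0.490. With SE = √(2/98) = 0.1429, the error is 1 − Φ(1.645 − 0.0102/0.1429) = 5.8%. This assumes quite different behaviour in the transferred patients, so it does not yield a break-even point against dropping. It does show that keeping them has a small cost of its own.

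**Hypoglycemia if transfers are kept.** The two groups side by side:

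- *Transferred CGM patient:* the named source is stored CGM data. On the worsening route the record ends when the sensor is removed. On the signal-loss route it ends before the move. Fingersticks direct care from then on but are not named as a source for the count.
- *Control:* evaluated during hourly ICU monitoring.

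The same gap arises, for shorter spells, in the 2-hour warm-up and after sensor removal for MRI or CT. The documents give no event rate, so the undercount cannot be sized.

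**The case against.** The strongest objection is that the natural reading already keeps everyone. The parenthesis after the group definition describes it by enrolment; 48 + 50 = 98 leaves no room for exclusions; ICU stay as an outcome would mean little for patients who never reach the ICU; and the Study Design wording describes intended care, not an exclusion rule. All of this stands. It makes retention the likelier reading, but none of it is a rule.

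A reader might go further and infer that the plan will exclude transfers, citing the two retrospective ICU patients. The documents do not support that. Those two are counted outside the 48, nothing says that they were ever on stepdown, and 2 of 50 cannot serve as a transfer rate.

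A reader might also take the larger table entries as the likely bias. They rest wholly on assumed counts and delays. Signal loss alone gives no clear reason for slow resolution, and the exclusion criteria already remove patients with another clinical reason for ICU admission.

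On hypoglycemia, it can fairly be said that the plan does not say CGM data are the *only* source, and that Study Procedures provides for chart review of all relevant data. But that general provision is not tied to this count, and the sentence that is tied to it names Clarity alone. Nor does the gap show that the overall comparison favours CGM: continuous readings may detect more episodes than hourly checks, which would work the other way. The claim is limited to periods without CGM data.

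**Conclusion.** The point holds as a gap in the plan, of minor to moderate severity. Exclusion of transferred patients is a possible reading, not the likely one. Bias toward non-inferiority requires three things together: transfers occur, they are dropped, and they resolve more slowly. The documents establish none of these as fact. With 2 of 98 dropped and an assumed excess of 1 to 2 SD, a one-sided 5% error rises to at most about 6.6% to 8.7%; with no excess there is no bias.

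The hypoglycemia part is firmer. Followed as written, the plan counts no episodes in a retained transferred patient once CGM data end, whereas ICU controls are counted under hourly monitoring. The direction for those patients is clear; the size is unknown.

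**What to change.** In Statistical Procedures:

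1. State that every prospective patient started on CGM for stepdown care is analysed in the CGM group for all outcomes (time to resolution, ICU stay, hospital stay, hypoglycemia and cost), including those later moved to the ICU. Give the stepdown-only result as a sensitivity analysis, since ICU care after transfer can dilute a difference.
2. State that for periods without CGM data, including after ICU transfer, hypoglycemia (<70 mg/dl) is counted from fingerstick values in the medical record.

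This takes a few sentences, with no added patients or visits; prospective patients' records are already to be abstracted. The costs are a little more chart abstraction, possibly a slightly less favourable CGM result, and some dilution in the main analysis. Recording the reason for each transfer, and stating whether the two retrospective ICU patients were ever on stepdown, would be useful detail, but the point does not depend on either.

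### Controls are selected by later ICU treatment while prospective CGM patients enter in the Emergency Department, and no common entry point, outcome clock or retention rule is given

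*Combined protocol and SAP*

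**What the plan says.** - **Controls.** Statistical Procedures describes them as "DKA patients who had glucose levels monitored hourly via fingerstick (and not CGM) and treated in the ICU setting". The retrospective part of Study Procedures describes them the same way. Neither place says that controls are identified at ED presentation or that the Inclusion and Exclusion Criteria apply to them.
- **CGM group.** The same sentence in Statistical Procedures limits the CGM group, retrospective and prospective, to patients treated in the stepdown unit. Study Design (Retrospective Quality Improvement Data) keeps 48 patients and leaves out 2 CGM patients because they were treated in the ICU.
- **Prospective entry.** Study Design plans "recruiting patients in the Emergency Department and offering them the opportunity to use DEXCOM G6 CGM". Under Study Procedures, consent and sensor placement take place in the ED, and step 3 adds "In the Emergency Department, document glucose levels q 2 hours as per the research protocol". Later moves to the ICU are foreseen, but their place in the analysis is not stated.
- **Analysis.** The plan says "We will compare with the historical control using 1:1 matching", with propensity matching on clinical factors associated with time to resolution. It uses "a noninferiority margin of 1/2 the SD" and states that "a sample size of 98 patients per group will have a 90% power". Time zero for the primary outcome is not defined in either group.

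**The concern.** A non-inferiority claim against non-randomised historical controls needs both groups defined at the same point in the care pathway. Here a control is recognised by an event that comes after presentation, namely treatment for DKA in the ICU. A control-era patient whose acidosis cleared while still in the ED never meets that description. A prospective CGM patient with the same course has already consented and is wearing the sensor.

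If that CGM patient is analysed, the control group has lost fast resolvers that the CGM group keeps. Matching on baseline factors cannot bring back someone who never entered the pool from which matches are drawn. The margin is half an SD, so a shift of a few tenths of an SD would take up much of it.

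**Working it through.** **The plan's own figure.** Margin 0.5 SD, power 90%, true difference assumed 0, alpha 0.05 with sidedness not stated. n per group = 2[(z₁₋α + z₀.₉₀)/0.5]².

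- One-sided 0.05: 2[(1.645 + 1.2816)/0.5]² = 68.5, so 69.
- One-sided 0.025: 2[(1.960 + 1.2816)/0.5]² = 84.06, so 85.

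The stated 98 does not follow from the stated inputs alone. It gives power Φ(0.5√49 − z), which is 96.8% or 93.8% respectively. Nothing below depends on this. Only n = 98 and the split 48 + 50 are carried forward.

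**Size of the shift with a common ED clock.** The documents give no resolution times, no ED waits and no share of patients who resolved in the ED, so all of these are assumptions. T is lognormal, CGM patients enter 2 h after presentation, and controls enter at ICU arrival, a hours after presentation. Then

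shift = {E[T | T > a] − E[T | T > 2]} / SD.

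For mean 12 h and SD 6 h, E[T | T > 2] = 12.00 h, and E[T | T > a] = 12.16, 12.87 and 14.13 h at a = 4, 6 and 8 h. The would-be controls lost are 2%, 11% and 27%. At 8 h the shift is (14.13 − 12.00)/6 = 0.35 SD, or 71% of the margin.

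ED recruitment is documented only for the 50 prospective patients. If the 48 retrospective patients were selected like the controls, the shift is multiplied by 50/98.

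| Mean, SD (h) | All CGM are ED entrants: 4 / 6 / 8 h | Only the 50 are: 4 / 6 / 8 h |
|---|---|---|
| 12, 6 | 0.03 / 0.15 / 0.35 SD | 0.01 / 0.07 / 0.18 SD |
| 14, 8 | 0.02 / 0.12 / 0.27 SD | 0.01 / 0.06 / 0.14 SD |
| 18, 9 | <0.01 / 0.03 / 0.09 SD | 0.00 / 0.01 / 0.05 SD |

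**If CGM patients must reach stepdown to count** (mean 12, SD 6). With stepdown reached 2 h before the ICU, the shift is 0.03, 0.12 and 0.21 SD at ICU arrival of 4, 6 and 8 h. With equal waits and the same distribution of T in both groups it is zero. With stepdown reached 2 h after the ICU it reverses: (12.16 − 12.87)/6 = −0.12 SD at 4 h and (12.87 − 14.13)/6 = −0.21 SD at 6 h.

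The cancellation needs equal true times. In a simulation with CGM slower by exactly the margin (lognormal, CV 0.6), a common cut-off that removes 5%, 10% or 20% of controls removes fewer CGM patients. It still moves the difference 0.07, 0.12 and 0.23 SD towards non-inferiority.

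**If the control clock starts at ICU arrival** while the CGM clock starts in the ED, a is subtracted from the control times. For mean 12, SD 6 and a = 6 the result is (12.87 − 6 − 12.00)/6, about −0.86 SD. Over all nine scenarios the range is −0.44 to −0.98 SD, which works against CGM.

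**Effect on false non-inferiority** (true inferiority equal to the margin, nominal one-sided 0.025, 98 per group, ED clock). Cut the fastest fraction f from a normal control distribution. With q = z_f, the shift is λ = φ(q)/(1 − f), the remaining variance is v = 1 + qλ − λ², and the error is Φ(λ/√[(1 + v)/98] − 1.96).

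| f | Shift (SD) | Error, controls only cut | Error, shift × 50/98 |
|---|---|---|---|
| 2% | 0.05 | 5.4% | 3.8% |
| 5% | 0.11 | 12% | 6% |
| 10% | 0.20 | 31% | 11% |
| 20% | 0.35 | 79% | 29% |
| 30% | 0.50 | 98% | 54% |

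The lognormal simulation with only controls cut gives 7%, 15% and 44% at f = 5%, 10% and 20%. The result is therefore sensitive to the shape assumed.

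**The case against.** A reader might infer that the plan builds in a one-sided bias favouring CGM. The documents do not support that, for four reasons.

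1. The sentence that defines the controls by ICU treatment also defines the CGM group by stepdown treatment. Read literally, a CGM patient who resolves in the ED is outside the comparison too. This stands: the asymmetry depends on a retention rule that the plan does not give.
2. ED recruitment is stated only for the 50 prospective patients; the other 48 are described by stepdown treatment. This stands, and it roughly halves the size.
3. With no time zero, the direction is open. This also stands. Setting a common clock alone would still leave the selection in place.
4. No fast resolvers are documented. Study Design says that DKA patients were treated in the ICU before the project, and the two-hourly ED recording gives a frequency, not a length of stay. If ICU transfer was quick or resolution slow, the effect is negligible, as the 4 h results show.

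A reader might also infer that pandemic ICU scarcity lengthened ED waits for the controls. The control period is not dated, and the plan describes ICU admission as the pre-pandemic standard that later resumed, so that step is not established.

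The objection does not remove the central gap. Controls who resolve before ICU arrival cannot be selected, and matching does not restore them.

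**Conclusion.** The point holds as a gap in how the groups are defined, with direction and size conditional. Both groups depend partly on later place of care, the 50 prospective patients enter in the ED, and no common entry point, clock or retention rule is given.

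Non-inferiority becomes easier to show if the clock starts in the ED for both groups and either ED-enrolled CGM patients are kept or stepdown is reached sooner than the ICU. Under the assumed times the shift then runs from about 0 to 0.35 SD, or about 0 to 0.18 SD if only the prospective patients are ED entrants, against a margin of 0.5 SD. A control clock at ICU arrival turns the net error against CGM.

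Leaving out the 2 ICU-treated CGM patients is a related selection that could favour CGM if they resolved more slowly; their resolution times are not reported. The plan should be changed before control data are extracted, because the choice of records decides which patients can be found.

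**What to change.** 1. Identify controls from ED encounters in a stated control period that meet the Inclusion and Exclusion Criteria and were managed on the hourly-fingerstick/ICU pathway, whether or not they reached the ICU.
2. Start the outcome clock at the same ED time point in both groups.
3. Analyse every CGM patient from sensor placement regardless of later unit, including those treated in the ICU, and state how the 48 retrospective patients were identified.
4. If ED-identified controls, or the entry point of the 48, cannot be recovered, analyse only patients in both groups who are still unresolved at one fixed number of hours after ED presentation.

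The cost is a changed record query, an extra timestamp and somewhat more chart review, with no new patients. The version in item 4 also shrinks the analysed set. It remains second best, because it conditions on an event after entry: as the simulation shows, a common cut-off does not fully cancel when CGM is truly slower.
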